#### 5.5.5 Vital Signs

The following vital signs will be recorded, before each DBPCFC and at any scheduled and unscheduled visits:

- Systolic blood pressure (in mmHg),
- Diastolic blood pressure (in mmHg),
- Heart rate (beats/minute),
- Respiratory rate (breaths per minute).

The following results will be tabulated for all vital signs:

- Summary statistics of values by visit and changes from Baseline
- Changes from Baseline by visit
- Number and percentage of subjects with vital signs abnormalities by post-baseline visit for heart rate, systolic blood pressure and diastolic blood pressure classified using the criteria defined in Table 8.

	Statistical Analysis Plan	
	EPITOPE (V712-304) – Statistical Analysis Plan	
	Référence du Document /Document Reference : CCI	Page : 58 / 74

CCI

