### 6.2.3 Vital Signs

The following vital signs will be assessed in accordance with the Schedule of Procedures (page 15):

- Blood pressure (systolic and diastolic; mmHg),
- Heart rate (beats per minute),
- Respiration rate (breaths per minute).

Systolic blood pressure and diastolic blood pressure will be measured in sitting position on the same arm after the subject has been resting.

Heart rate will be recorded simultaneously with blood pressure measurements, followed by respiratory rate.

During the study, the measurement of vital signs may be repeated at the discretion of the Investigator for safety reasons. Clinically relevant abnormal findings will be reported as AEs.

Vital signs must be assessed before the DBPCFC. Additional assessments can be repeated during the DBPCFC procedure on both days at any time if judged necessary by the Investigator.

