	EPITOPE (V712-304) – Statistical Analysis Plan	
	Référence du Document /Document Reference : CCI	Page : 13 / 74

CCI

PC = Phone contact; SCORAD = Scoring atopic dermatitis; SPT = Skin prick test; UV = Unscheduled Visit; V = Visit.

- 1 If the subject has a concomitant disease which temporarily contra-indicates the performance of the DBPCFC, the test is to be postponed until at least 7 days after recovery
- 2 Visit 4 may take place on the same day as Visit 3, but this would result in a very long day for the subject (parents/guardians) as all Visit 4 procedures would then have to take place that same day.
- 3 The Visit 7bis was to be conducted for Part A subjects only in the eventuality of a dose switching for safety reason. After review of the 3-month safety data, both doses of DBV712 were considered as safe, and no dose switching is required. As a consequence, Visit 7bis will not be performed.
- 4 Visit 12 will take place only for subjects not rolling over into the extension follow-up study
- 5 Unscheduled Visit could be conducted in case of AEs, need for treatment re-supply, etc. Procedures will be optional and performed as deemed necessary by the investigator.
- 6 At V1, all selection criteria could be verified except for those that depend on the results of the immunological markers testing (peanut-specific IgE) and on the outcome of the entry/screening DBPCFC.
- 7 Including history of peanut allergy.
- 8 Including a complete skin examination, body weight and height.
- 9 Blood pressure, heart rate and respiratory rate.
- 10 These examinations are to be done before the DBPCFC. Additionally, they can be repeated during the DBPCFC procedure on both days anytime if judged necessary by the Investigator.
- 11 Peanut-specific IgE, peanut-specific IgG4, peanut-specific IgE and peanut specific IgG4 to Ara h 1, Ara h 2, Ara h 3, and total IgE will be evaluated at Visits 1, 7, 8, 10. Total IgE will be assessed in Part B subjects only. IgE specific to cow's milk, egg white, house dust mites, and grass pollen will be assessed at Visit 1 and Visit 10 only and in case of an early termination visit.
- 12 Laboratory tests performed centrally. Hematology: hemoglobin, hematocrit, platelets, red blood cells, white blood cells with differential cell count. Biochemistry: aspartate aminotransferase, alanine aminotransferase, total bilirubin, total protein, blood urea nitrogen, creatinine.

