	Référence du Document /Document Reference : CCI	Page : 26 / 74

CCI

For summaries and listings of shift from baseline and potentially clinically significant values, all values will be considered in the analyses.

All data collected at unscheduled visits will be listed.

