#### 5.5.6 Physical Examination

A Physical examination will be performed, in accordance with the Schedule of Procedures and includes the following parameters and at any unscheduled visit at the discretion of the investigator.

Physical examination will include the measure of the weight (kg) and height (cm) and the examination of the following:

- General appearance,
- Head and Neck,
- Ears, nose and throat,
- Eyes,
- Complete skin examination,
- Cardiovascular system,
- Respiratory system,
- Abdominal system,
- Nervous system,
- Other system(s).

	Statistical Analysis Plan	
	EPITOPE (V712-304) – Statistical Analysis Plan	
	Référence du Document /Document Reference : CCI	Page : 59 / 74

CCI

The following results will be tabulated:

- Summary statistic for weight and height by visit and change from Baseline,
- Number and percentage of subjects with abnormal (vs. normal / not done) physical examination by visit for each of the system examined.

Physical examination data will also be listed for the Safety set.

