## 5.6 Study Procedure Safety Evaluation

The symptoms elicited during the DBPCFC (as they are expressly provoked) are differentiated from TEAEs and Treatment Emergent SAEs.

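### The Month 12 vital-sign tables are not limited to the pre-challenge reading, so changes provoked by the peanut challenge can appear as patch-safety findings at Visits 10 and 11

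*SAP*

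**What the plan says.** SAP 5.5.5 sets the collection rule: "The following vital signs will be recorded, before each DBPCFC and at any scheduled and unscheduled visits". It then tabulates values and changes from baseline by visit, and "Number and percentage of subjects with vital signs abnormalities by post-baseline visit for heart rate, systolic blood pressure and diastolic blood pressure", using the limits in SAP Table 8.

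On challenge days the required reading comes first: "Vital signs must be assessed before the DBPCFC" (protocol 6.2.3). The same section allows more: "Additional assessments can be repeated during the DBPCFC procedure on both days at any time if judged necessary by the Investigator". Footnote 10 to the SAP flow chart repeats this for vital signs and physical examination: "Additionally, they can be repeated during the DBPCFC procedure on both days anytime if judged necessary by the Investigator".

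SAP 5.2.7 decides which readings are analysed. For safety it uses re-tests and unscheduled data. Where a vital sign is measured more than once on a day, it takes the later one. It adds: "For summaries and listings of shift from baseline and potentially clinically significant values, all values will be considered in the analyses".

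Elsewhere the SAP keeps challenge reactions apart from patch safety. Section 5.6 says: "The symptoms elicited during the DBPCFC (as they are expressly provoked) are differentiated from TEAEs and Treatment Emergent SAEs". Section 5.5.1.3 removes challenge SAEs from the adverse-event analyses and tabulates challenge symptoms separately.

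**The concern.** The vital-sign tables belong to the study-drug safety section and will be read as evidence about the patch. A child who reacts to peanut on a challenge day may have a fast pulse or a fall in blood pressure because of the peanut. A heart-rate rise of more than 20 beats/min from pre-dosing is enough to meet SAP Table 8. If such a reading enters the Month 12 row, the row mixes the effect of the patch with the effect of the challenge and cannot be read as patch safety. A real patch effect could be diluted, or a difference between arms could arise from the challenge alone.

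**Working it through.** No figure in the plan bears on this point, so the check is mainly a reading of the rules side by side.

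**1. Can in-challenge readings exist?** Yes. Both documents allow repeats during the challenge on both days.

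**2. Would the tables take them?**
- *Values and changes from baseline.* Two readings on the same day are equally far from the target day, and SAP 5.2.7 takes the later one. An in-challenge repeat would replace the pre-challenge reading.
- *Abnormality counts.* SAP 5.2.7 uses all values for potentially clinically significant values. SAP 5.5.5 calls its criteria clinically relevant abnormalities, so the terms do not match exactly. Either reading admits the repeat: it counts alongside the earlier reading, or it replaces it under the same-day rule.

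**3. Does anything keep them out?** SAP 5.5.1.3 and 5.6 cover challenge SAEs and symptoms and do not mention vital signs. Protocol 8.2.2.3 sends vital signs obtained at non-protocol visits, or while investigating or managing AEs, to listings only. Visits 10 and 11 are protocol visits, and protocol 6.2.1.3.6 says challenge symptoms are not reported as single AEs, so its reach is unclear. SAP 5.2.7 uses re-tests and unscheduled data for safety, which conflicts with it, and none of the six changes in SAP 5.11 mentions this.

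**4. Which rows?** Only Month 12 (V10) and Month 12 (V11), which are separate analysis visits in SAP Table 2. Day 8 and Months 1 to 9 precede the post-treatment challenge. Protocol 6.1.1.2 randomises the order of peanut and placebo days, so peanut-day readings are split between the two rows.

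**5. Illustration with assumed inputs.** Let b be the share of children abnormal for reasons unrelated to the challenge, r the share reacting, and c the share of reactors with an abnormal in-challenge reading in the data. The documents give none of these. Treating the two causes as independent,

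P(abnormal) = 1 − (1 − b)(1 − c·r).

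Take b = 5% on placebo and 15% on active, a true difference of 10 points. With r = 95% in both arms, the observed difference is 10 × (1 − 0.95c):
- c = 10%: 10 × 0.905 = 9.05 points
- c = 30%: 10 × 0.715 = 7.15 points
- c = 50%: 10 × 0.525 = 5.25 points

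Mixing therefore dilutes the difference even when reaction rates are equal. If they differ, the result depends on how (active minus placebo, in points):

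| Assumption | c = 10% | c = 30% | c = 50% |
|---|---|---|---|
| r = 95% placebo, 85% active | 8.2 | 4.6 | 1.0 |
| r = 95% placebo, 70% active | 6.9 | 0.8 | −5.4 |
| r = 95% placebo, 85% active; c 1.3 times as high on active | 10.4 | 11.1 | 11.8 |

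For example, in the first row at c = 50%, placebo is 1 − 0.95 × 0.525 = 50.1% and active is 1 − 0.85 × 0.575 = 51.1%.

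These figures put every peanut day in one row. If the day order is balanced 1:1 (an assumption), c·r is halved in each row. The equal-rate differences become 10 × (1 − 0.0475) = 9.5 points at c = 10% and 10 × (1 − 0.2375) = 7.6 points at c = 50%.

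**The case against.** The strongest objection is that the problem may never arise. The required challenge-day reading is the pre-challenge one, repeats are discretionary, and neither document says that repeats go on the vital-signs form. The challenge-page items listed in protocol 6.2.1.3.6 do not include vital signs, which leaves their destination open. The tables are descriptive, and a patch effect would still be visible at earlier visits. All of this stands. It makes the point conditional and minor, but does not supply the missing rule.

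A reader might go further in three ways that the documents do not support.

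- **That provoked abnormalities must be commoner on placebo and so hide a drug effect.** One might turn the planned 40% and 10% response rates into 60% and 90% reacting. But response means reaching a target eliciting dose. Both arms escalate to a stopping reaction or 2,000 mg, so a responder can still react, at a higher dose. The planned rates also count missing challenges as failures, with drop-out of up to 15%, and a child who was never challenged has no in-challenge reading. The bias could run either way.
- **That the SAP breaks its own rule.** The separation rules name symptoms and adverse events. For vital signs there is a gap that is at odds with their purpose, not a breach.
- **That baseline is contaminated when Visits 3 and 4 fall on one day.** Visit 4 has its own vital signs and baseline is the latest pre-dose value, so the Visit 4 reading normally supersedes any in-challenge one.

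The case for physical examination is also weaker. SAP 5.5.6 reports "Number and percentage of subjects with abnormal (vs. normal / not done) physical examination by visit for each of the system examined", and examinations may be repeated during the challenge, but the same-day rule names only laboratory and vital-sign parameters.

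**Conclusion.** The point holds, as a minor one. Followed as written, the SAP's selection rules would put any in-challenge vital sign held in the vital-signs data into the Month 12 (V10 and V11) patch-safety rows, in place of or alongside the pre-challenge reading. This assumes that such repeats are taken and entered as vital-sign records. Within those rows the arm comparison can be diluted or distorted. Direction and size cannot be derived from the documents; the illustration shows only that both depend on inputs they do not give. The unreconciled difference between SAP 5.2.7 and protocol 8.2.2.3 is a further reason to settle the rule.

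**What to change.** In SAP 5.5.5, and in 5.5.6 for consistency, state that at Visits 10 and 11 only the last assessment before that day's first challenge dose enters the by-visit summaries, changes from baseline and abnormality counts. Say explicitly that this is an exception to the same-day and all-values rules in 5.2.7. Present in-challenge readings under SAP 5.6, by formula (peanut or placebo) and by arm. Reconcile 5.2.7 with protocol 8.2.2.3 and record the outcome in 5.11.

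The cost is SAP wording and one selection flag. The flag needs the time of each reading relative to the first challenge dose, or a pre-challenge label, so check before database lock that one of these is recorded. No new assessments are needed. The small downside is that in-challenge readings move from the patch-safety tables to the challenge section.

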**Table 8 - Criteria to Determine Clinically Relevant Abnormalities in Vital Signs**

Vital Sign Criteria for Abnormalities	Criteria for Abnormalities (any of the following situation)
Heart rate	
 
• value <60 beats/min,
 
• value >130 beats/min,
 
• an increase from pre-dosing of >20 beats/min, or
 
• a decrease from pre-dosing of >20 beats/min
 

Systolic blood pressure	
 
• value <70 mmHg
 
• value >130 mmHg,
 
• an increase from pre-dosing of > 40 mmHg, or
 
• a decrease from pre-dosing of >30 mmHg
 

Diastolic blood pressure	
 
• value <45 mmHg
 
• value >85 mmHg,
 
• an increase from pre-dosing of >30 mmHg, or
 
• a decrease from pre-dosing of >20 mmHg
 

Vital signs data and clinically relevant abnormalities in vital signs will also be listed.

#### 5.5.6 Physical Examination

A Physical examination will be performed, in accordance with the Schedule of Procedures and includes the following parameters and at any unscheduled visit at the discretion of the investigator.

Physical examination will include the measure of the weight (kg) and height (cm) and the examination of the following:

- General appearance,
- Head and Neck,
- Ears, nose and throat,
- Eyes,
- Complete skin examination,
- Cardiovascular system,
- Respiratory system,
- Abdominal system,
- Nervous system,
- Other system(s).

	Statistical Analysis Plan	
	EPITOPE (V712-304) – Statistical Analysis Plan	
	Référence du Document /Document Reference : CCI	Page : 59 / 74

CCI

The following results will be tabulated:

- Summary statistic for weight and height by visit and change from Baseline,
- Number and percentage of subjects with abnormal (vs. normal / not done) physical examination by visit for each of the system examined.

Physical examination data will also be listed for the Safety set.

## 5.6 Study Procedure Safety Evaluation

The symptoms elicited during the DBPCFC (as they are expressly provoked) are differentiated from TEAEs and Treatment Emergent SAEs.

### 5.6.1 Serious Adverse Events Elicited during DBPCFC

All SAEs elicited during the entry/screening DBPCFC and Month 12 DBPCFC will be tabulated by SOC / PT and by timepoint. It will be discriminated between Peanut- and Placebo-Formula.

SAE elicited during any DBPCFC during the study will also be listed on the Enrolled Set.

### 5.6.2 Symptomatic Reactions during DBPCFC

The objective symptoms collected during the DBPCFC are the following:

- Skin:
  - Erythematous rash (and % of rash area concerned)
  - Pruritus
  - Urticaria/ angioedema
  - Rash
- Upper respiratory:
  - Sneezing/ itching
  - Nasal congestion
  - Rhinorrhea
  - Laryngeal
- Lower respiratory:
  - Wheezing
- Gastrointestinal:
  - Diarrhea
  - Vomiting
  - Cardiovascular
- Eyes:

CONFIDENTIEL / Ne pas diffuser sans autorisation de DBV

CONFIDENTIAL / Do not distribute without DBV authorization

	Statistical Analysis Plan	
	EPITOPE (V712-304) – Statistical Analysis Plan	
	Référence du Document /Document Reference : CCI	Page : 60 / 74

CCI

- Conjunctivitis
- Any other objective symptoms (not reported, mild, moderate, severe)

The subjective symptoms collected are:

- Itchy mouth
- Itchy throat
- Nausea
- Abdominal pain
- Any other subjective symptoms (not reported, mild, moderate, severe).

With the exception of erythematous rash (recorded as Yes/No), each symptom is graded as: 0=" absent", 1=" mild", 2=" moderate" or 3=" severe". For erythematous rash, the % area involved is collected. The grading corresponding to the area involved is captured in the grading of the "Rash" symptom. No further step is required.

A total symptom score for each subject will be calculated as the sum of all severity score for all objective symptoms (for the Peanut formula only, excluding erythematous rash) and abdominal pain subjective symptom (only when grade is 2 or 3). This will be based on the sum of each of the following symptom being graded for severity as 0, 1, 2 or 3 (respectively absent, mild, moderate and severe):

Pruritus, Urticaria/ angioedema, Rash, Sneezing/ itching, Nasal congestion, Rhinorrhea, Laryngeal, Wheezing, Diarrhea, Vomiting, Cardiovascular, Conjunctivitis, Abdominal pain, Any other objective symptoms (one score for each of the other objective symptoms, 0 if no other objective symptom is recorded or if the answer to the question "Did the subject experienced any objective symptoms" is "No").

The reactions appearing during a DBPCFC will be summarized by group and by formula (peanut, placebo) for the enrolled set, showing:

- The number and percentage of subjects with objective symptoms (by severity) at Baseline and at Month 12 (actual value) (overall and by type of symptom)
- The number and percentage of subjects with subjective symptoms (by severity) at Baseline and at Month 12 (overall and by type of symptom)
- Summary statistics on the Total symptom score at Baseline, at Month 12 (actual value) and the change from Baseline to Month 12 (using observed values).
- Symptoms used to calculate the Total symptom score will also be described using the number and percentage of subjects with symptoms by maximum severity at Baseline and at Month 12 overall and at each dose of DBPCFC. The Month 12 maximum symptom severity in the selected active DBV712 group (250 µg) compared to the placebo group will be analyzed on the FAS set excluding subjects with intercurrent events 1, 2 or 5 using a Cochran-Armitage Trend Test.

CONFIDENTIEL / Ne pas diffuser sans autorisation de DBV

CONFIDENTIAL / Do not distribute without DBV authorization

	Statistical Analysis Plan	
	EPITOPE (V712-304) – Statistical Analysis Plan	
	Référence du Document /Document Reference : CCI	Page : 61 / 74

CCI

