### 3.3.2 Safety Criteria

The following IMP safety criteria will be evaluated:

- AEs and treatment-emergent adverse events (TEAEs) by System Organ Class (SOC) and Preferred Terms (PTs);
- TEAEs by maximum severity and relatedness to DBV712;
- Incidence, duration and maximum severity of local cutaneous DBV712-induced AEs as assessed by the subject;
- Incidence and severity of local cutaneous DBV712-induced AEs as assessed by the Investigator;
- Local adverse events of special interest (AESIs) (i.e., reactions at patch sites potentially leading to skin barrier disruption) and systemic AESIs (i.e. anaphylaxis, or systemic hypersensitivity reactions leading to epinephrine intake), whatever the causal relationship to the IMP;
- SAEs by SOC and PTs, and relatedness to DBV712;
- Laboratory data, physical examinations and vital signs;

In addition, the following study procedure safety criteria will be evaluated:

- Symptoms elicited during the entry/screening DBPCFC and post-treatment DBPCFC at Month 12 by severity;
- Change in severity of symptoms elicited during the DBPCFC from baseline to Month 12 in the selected active DBV712 group (250 µg) *versus* the placebo group;
- SAEs elicited during the entry/screening DBPCFC and post-treatment DBPCFC at Month 12.

Details of the assessment of each of the safety criteria are provided in Section 6.2 and details of the corresponding statistical analysis are provided in Section 8.6.

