#### 4.1 Inclusion Criteria

Subjects will be enrolled only if they meet all of the following criteria:

1. Male or female from 1-3 years of age at Visit 1.
2. Physician-diagnosed peanut allergy or high suspicion of peanut allergy as assessed by the physician: child presenting signs, symptoms and a medical and/or a family history putting him/her at high risk of having a peanut allergy and/or history of presence of peanut-specific IgE and/or positive SPT.
3. Subject currently following a strict peanut-free diet.
4. Signed informed consent of parent(s)/guardian(s) of the children aged 1-3 years.
5. Peanut-specific IgE level (ImmunoCAP system) > 0.7 kU/L.
6. Positive peanut SPT with a largest wheal diameter  $\geq 6$  mm.
7. Positive DBPCFC to peanut, with symptoms meeting the challenge stopping criteria at an ED  $\leq 300$  mg peanut protein.
8. Parents/guardians and subjects willing to comply with all study requirements during their participation in the study.

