#### 4.2 Exclusion Criteria

Subjects will be enrolled only if they meet none of the following exclusion criteria:

1. Peanut allergic subjects presenting a medical history of severe anaphylaxis to peanut will be excluded for this study. Severe anaphylaxis is defined by the Grade 3 of the Anaphylaxis Staging System (APPENDIX 4), including:
  - Severe hypoxia, persistent hypotension or more than 20% drop in blood pressure, neurological compromise, or
  - Cyanosis or SpO2  $\leq 92\%$  at any stage, confusion, cardiovascular collapse, loss of consciousness, bradychardia, cardiac arrest.
2. Severe reaction during the entry/screening DBPCFC, defined as any of the following:
  - Need for intubation
  - Hypotension persisting after epinephrine administration
  - Need for three doses or more of systemic epinephrine.
3. Subject with reactions to the placebo formula during the screening DBPCFC (with reactions deemed to stopping the challenge).
4. Subjects who fail to complete the entry food challenge due to any reason including clear aversion to the food formula matrix,
5. Subject with any clinically significant abnormality identified at the time of screening such as major infantile infectious diseases (pox, measles) which in the judgment of the Investigator can preclude safe participation or strict compliance to the protocol procedures. Subjects can be considered for the study after recovery from these diseases.
6. Viral upper respiratory infection or gastroenteritis or any severe disease within 7 days of food challenge (challenge must be rescheduled at least after 7 days upon recovery).

7. Hypersensitivity to any of the Viaskin® patch components (except to peanut protein), including the adhesive film.
8. Hypersensitivity to any component of the food challenge formula (except to peanut protein) or a known history of apple allergy.
9. Inability to discontinue short-acting antihistamines or long-acting antihistamines for the minimum wash-out periods required (depending on half-lives and specified in [APPENDIX 3](#)) prior to the skin prick testing or the food challenges.
10. Diagnosis of asthma that fulfills any of the following criteria:
  - Uncontrolled asthma (as per Global Initiative for Asthma [GINA] latest guidelines; see [APPENDIX 8](#))

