#### 6.2.1.3.6 Symptoms during to the Double-blind, Placebo-Controlled Food Challenge

The severity of the objective and subjective symptoms elicited during the entry and post-treatment DBPCFC will be assessed by the Investigator. These objective and subjective symptoms assessed by the Investigator will not be reported as single independent AE in the AE pages of the e-CRF. Complete information for all these symptoms will be reported in the DBPCFC pages of the e-CRF, along with all peanut protein doses given, the symptoms observed, the time of appearance of the symptoms and their specific grades, the time of grade change of each symptom, the doses of epinephrine given, the doses of corticosteroids and antihistamines given and the Investigator's assessment of the peanut ED as well as the peanut cumulative dose. If, as per the Investigator's judgment, the combination of all these symptoms resulted in an anaphylaxis requiring a prolonged (minimally overnight) hospitalization, then this will be considered an SAE. Any such SAE with its specific verbatim (e.g. 'during food challenge' or 'due to food challenge') must be reported in the AE pages of the e-CRF.

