#### 8.6.7 Symptomatic Reactions during the DBPCFC

The incidence of objective and subjective symptoms/reactions elicited during the DBPCFCs will be summarized. A severity score based on the grades of symptoms elicited during the DBPCFCs will be described at baseline and at Month 12. The change in the severity score from baseline will also be presented.

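### The between-arm test of Month 12 challenge symptom severity has no baseline term; stratifying it by entry-challenge severity costs nothing and may add power

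*SAP*

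**What the plan says.** Protocol 3.3.2 and SAP 3.3 list, among the study-procedure safety criteria, "Change in severity of symptoms elicited during the DBPCFC from baseline to Month 12 in the selected active DBV712 group" against placebo. Protocol 8.6.7, the analysis section for challenge reactions, handles this descriptively: a severity score is described at both time points and "The change in the severity score from baseline will also be presented".

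SAP 5.6.2 has two strands.

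- **Total symptom score:** summary statistics, including "the change from Baseline to Month 12 (using observed values" only).
- **Maximum severity:** counts at baseline and Month 12, followed by one inferential comparison. "The Month 12 maximum symptom severity in the selected active DBV712 group" is compared with placebo on the FAS, "excluding subjects with intercurrent events 1, 2 or 5 using a Cochran-Armitage Trend Test". No baseline covariate or stratum is named.

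SAP 5.11 records that analysis of challenge symptoms was added relative to the protocol.

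Baseline severity is available by design. Protocol 4.1 requires a "Positive DBPCFC to peanut, with symptoms meeting the challenge stopping criteria at an ED" of 300 mg or less. Protocol 4.2 excludes "Subjects who fail to complete the entry food challenge due to any reason including clear aversion to the food formula matrix". Protocol 6.2.1.3.6 says: "The severity of the objective and subjective symptoms elicited during the entry and post-treatment DBPCFC will be assessed by the Investigator".

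**The concern.** The listed criterion is about change since the entry challenge, but the p-value that will be reported concerns Month 12 alone. Children differ in how severely they react. If that tendency persists over a year, part of the Month 12 spread is predictable from the entry challenge, and a test that ignores it gives up precision. Any difference between arms in entry severity would also carry partly into the Month 12 comparison.

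The tested set is smaller than the randomised set, because children in intercurrent events 1, 2 and 5 drop out of it. Balance at baseline therefore rests less securely on randomisation. What is at stake is the reading of a supportive safety result: whether treated children react less severely when challenged.

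**Working it through.** **1. Passages side by side**

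| Item | Variable | Between-arm analysis |
|---|---|---|
| Criterion (Protocol 3.3.2, SAP 3.3) | change in symptom severity, entry to Month 12 | worded as active versus placebo; no test specified |
| Protocol 8.6.7 | severity score and its change | described |
| SAP 5.6.2, total score | baseline, Month 12, change | summary statistics |
| SAP 5.6.2, maximum severity | Month 12 only | Cochran-Armitage test, no baseline term |

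**2. Inputs.** The documents give no power, effect size or sample size for this test, so there is no figure to reproduce. For an illustration:

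- Evaluable children: 233 × 0.85 ≈ 198 and 117 × 0.85 ≈ 99, from the Part B numbers and the 15% maximum drop-out in the protocol synopsis.
- Assumed: a latent shift of 0.35 SD, and a latent baseline-to-Month-12 correlation ρ of 0 to 0.6.
- Assumed: baseline maximum severity graded 1 to 3 in proportions 25/60/15%, and Month 12 placebo severity graded 0 to 3 in proportions 5/30/50/15%.

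**3. Chance imbalance in baseline severity.** The standard error of the standardised difference is √(1/198 + 1/99) = 0.123, so the 95% range is ±1.96 × 0.123 = ±0.24 SD. This assumes the evaluable arms still behave like random samples. An imbalance carries into Month 12 in proportion to ρ, so one at the edge of that range shifts Month 12 by 0.24ρ: 0, 0.05, 0.10 and 0.14 SD at ρ = 0, 0.2, 0.4 and 0.6.

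**4. Variance relative to Month 12 alone.** Baseline-adjusted: 1 − ρ². Raw change score: 2(1 − ρ).

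| ρ | adjusted | raw change |
|---|---|---|
| 0 | 1.00 | 2.00 |
| 0.2 | 0.96 | 1.60 |
| 0.4 | 0.84 | 1.20 |
| 0.6 | 0.64 | 0.80 |

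A raw change-score test is less precise than Month 12 alone whenever ρ is below 0.5. Adjustment is not.

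**5. Simulated power** (198:99, 4,000 trials per setting, two-sided 5%; Monte Carlo error √(0.74 × 0.26/4000) ≈ 0.7 points)

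| ρ | unadjusted trend test | stratified by baseline | raw change test | gain from stratifying |
|---|---|---|---|---|
| 0 | 74.4% | 73.8% | 53.3% | −0.6 |
| 0.2 | 73.7% | 74.4% | 59.4% | +0.7 |
| 0.4 | 73.5% | 77.3% | 68.6% | +3.8 |
| 0.6 | 74.3% | 84.2% | 80.1% | +9.9 |

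With no treatment effect (2,000 trials per setting), rejection was between 3.75% and 5% for all three tests. Two further simulations under similar assumptions, one with 198:99 and one with 205:103, agree at ρ up to 0.4 and gave gains of 12 and 11 points at ρ = 0.6.

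**6. What the stratified test measures.** Within a stratum all children share one baseline grade b, so Month 12 grade Y and change Y − b differ by a constant. With equally spaced scores, subtracting a constant leaves the stratum's numerator and variance unchanged. The stratified trend test is therefore also a test of change in maximum severity.

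**The case against.** The case for leaving the plan alone has weight.

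- A reader might infer that the SAP neglects its own criterion. The documents do not support that. Neither list of criteria asks for a test, Protocol 8.6.7 plans description only, and SAP 5.6.2 supplies it by group. The trend test is a separate addition on a different variable. Baseline maximum severity is tabulated, so an imbalance would be visible.
- A reader might infer that the exclusions spoil the test and that adjustment repairs it. Events 1, 2 and 5 are by definition children without a Month 12 peanut challenge (SAP Table 3), so they have no Month 12 severity to analyse. The adjusted test omits the same children, and one covariate does not restore the randomised comparison.
- A reader might infer that a baseline difference passes in full into the result. It passes only in proportion to ρ, and ρ could be modest. Both challenges stop once set criteria are met, which narrows the range of severity, and the top dose is 300 mg at entry but 2,000 mg at Month 12.
- A reader might infer a breach of the SAP's baseline-covariate rule. SAP 5.2.5 states that rule for continuous variables, and the primary responder difference is itself unadjusted.

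All four replies stand. None gives a reason to prefer the unadjusted test: the baseline grade is collected, and using it costs essentially nothing even when it is uninformative. The remedy leaves the total-score change untested, but it does test change in maximum severity (step 6).

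**Conclusion.** The point holds as an optional improvement. The one visible between-arm test of challenge symptom severity ignores a baseline value that should exist for every randomised child, barring protocol deviations, and that bears on the listed criterion. Power changes by 1 point or less at correlations of 0 to 0.2, and rises by about 4 points at 0.4 and 10 to 12 at 0.6. These figures rest on an assumed correlation, a 0.35 SD shift, assumed severity distributions and roughly 198:99 evaluable children. The documents give none of the first three, and the fourth is derived from the planning drop-out rate.

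The test lies outside the testing hierarchy (SAP Table 1) and has no success criterion, so no primary or secondary conclusion depends on it. Calling it the one test refers to the readable text; parts of the SAP, including its appendices, are not shown.

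**What to change.** In SAP 5.6.2, make the between-arm comparison of Month 12 maximum severity a trend test stratified by baseline maximum severity (extended Mantel-Haenszel row-mean-score test, equally spaced scores). A proportional-odds model with treatment and baseline maximum severity would serve equally. Keep the unadjusted Cochran-Armitage test as supportive and the total-score change summary as planned. Do not substitute a raw change-score test, which loses precision if the correlation is below 0.5. State that the analysis covers only children with a Month 12 peanut challenge and that adjustment does not undo that selection.

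Cost: about one line of SAP text and one of code, before unblinding. No new data are needed.
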